4.3 Protocol Deviations

All protocol deviations will be determined prior to database lock and will be agreed upon by a review of individual subject data.

The pre-defined important CSR-reportable protocol deviations are listed below; in addition, any other protocol deviations deemed by ADCT medical to be important CSR-reportable deviations will be included in the summary.

1. Patient entered the study even though they did not satisfy the entry criteria.
2. Patient received a prohibited concomitant treatment during the study.
3. Patient who met criteria for mandatory study drug discontinuation during the study but did not have study drug withdrawn.
4. Patient who received the wrong treatment or incorrect dose, specifically:
 - Actual dose of study drug was greater than 15% more or less than protocol defined planned dose level.
 - Patient started next cycle less than 18 days after Day 1 of the most recent treatment cycle.

Important protocol deviations will be listed in patient level.

4.4 Demographic and Baseline Characteristics

Demographic information will be summarized. The summary will include age and age groups (≥ 65 , <80), (≥ 80), sex, Ethnicity, race and race groups.

The baseline characteristics will be summarized. The baseline characteristics will include cumulative illness rating scale for geriatrics (CIRS-G), Katz activities of daily living (ADL scales), and Lawton- Brody instrumental activities of daily living scale (IADL scales). The three categories of fit, unfit, and frail will be derived from the three rating scales. The patient level rating scales and derived sGA categories will be listed.

Demographic and baseline characteristics data will also be listed at patient level.

4.5 Cancer History and Medical History

Cancer history, including primary category per WHO 2016 classification, method used to designate cell of origin for DLBCL subtype, disease staging, and additional subtype information will be summarized.

Prior systemic treatments for iNHL, including number of lines, response to the first/most recent line, prior radiotherapy will be summarized.

Cancer history and medical history will be listed.

Prior systemic therapy and radiotherapy will be listed.

4.6 Prior and Concomitant Medications (other than anticancer therapies)

All medications will be recorded in the CRF starting from the ICF signature date or from 14 days prior to C1D1, whichever is earlier, and continuing until 30 days after last dose of study drug.

All medications will be coded using the World Health Organization-Drug Dictionary (WHO-DD).

- Prior medications are those the patient used prior to the first dose. Prior medications can be discontinued before the first dose or can be ongoing during the treatment phase.
- Concomitant medications are any treatments received by the patient concomitantly to any loncastuximab tesirine from the first dose to the last dose + 30 days. A given medication can be classified both as a prior medication and as a concomitant medication. Concomitant medications do not include medications started 30 days after the last dose.

Prior and concomitant medications will be listed in patient level.

4.7 Exposure to Treatment

4.7.1 Extent of Study Drug Exposure

Study drug exposures will be based on the All-treated population.

A treatment cycle is defined as 3 weeks (i.e., 21 days).

Duration of treatment, total number of cycles dosed, total dose received), average dose per cycle, and relative dose intensity (actual dose taken / planned dose) will be summarized. Dose administered at each infusion is calculated by concentrated investigational product (IP) volume (in mL)* concentration. For incomplete infusion, actual dose will be adjusted by proportion of volume of dosing solution administered.

Relative dose intensity will be additionally presented categorized (<60%, >=60 - <80%, >=80 - <90%, >=90 - <110%, >=110%).

Exposure data and infusion details will be listed together.

4.7.2 Prophylactic Medications for Hypersensitivity

Prophylactic medications for hypersensitivity will be listed only.

4.7.3 Subsequent Anticancer Therapy or Procedure

Patients' subsequent anticancer therapies or procedures including systemic therapy, radiation, transplant, or other, along with the start date of new anticancer therapy or procedure will be collected and listed only.

4.8 Efficacy Analyses

Efficacy analyses will be based on response as determined by investigator with the All-treated population. The endpoints for efficacy include Complete Response Rate (CRR), Overall Response Rate (ORR) according to the 2014 Lugano classification as determined by investigator (See Lugano classification in Appendix x), Duration of Response (DoR).

All efficacy endpoints and tumor assessment data will be listed in patient level.

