2.2 Rationale for Dose Selection

In the pivotal monotherapy Phase 2 study for R/R DLBCL, ADCT-402-201, loncastuximab tesirine was dosed every 3 weeks, with 150 µg/kg for first two cycles and 75 µg/kg for the subsequent cycles, which resulted in a high level of efficacy and was well tolerated. In addition, PK analyses show that this dosing regimen resulted in comparable exposure between Cycle 1 and subsequent cycles and that this dosing regimen resulted in consistent drug exposure across cycles. The dosing regimen chosen for this study is based on the regimen of loncastuximab tesirine used in the Phase 2 study. This study will utilize the same dosing regimen for Lonca-R as the ongoing Phase 3 clinical trial LOTIS-5 comparing the Lonca-R regimen (after a safety run-in) to R-GemOx in 2L transplant-ineligible patients with DLBCL. Treatment-naïve patients will present with levels of lymphocytes (within normal limits) which are believed to function as an antigen sink to loncastuximab tesirine. Administration of rituximab is known to reduce lymphocytes levels within a day ([Blasco, 2009](#)). Therefore, loncastuximab administration in Cycle 1 is given 1 day (+2 days) after rituximab administration.

3 Study Objectives and Endpoints

Table 3 Study Objectives and Endpoints

Objectives	Endpoints
Primary	
Cohort A To assess the efficacy of a response-adapted treatment of Lonca-R in unfit patients with previously untreated DLBCL or HGBCL or Grade 3b FL.	(Co-)Primary Endpoints: Cohort A CR rate, defined as proportion of patients with a BOR of CR according to the 2014 Lugano Classification criteria (Appendix 12.2). Cohort B 
• CR rate, defined as proportion of patients with a BOR of CR according to the 2014 Lugano Classification criteria.• Tolerability as defined by the percentage of patients completing a total of 4 cycles of therapy divided by the total number of patients.
Secondary	

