9.4 Final Analysis

All efficacy and safety endpoints will be analyzed and reported in the clinical study report (CSR).

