SoC	standard of care
SoE	schedule of events
TEAE	treatment-emergent adverse event

1 Introduction

This statistical analysis plan (SAP) describes the statistical methods to be used during the reporting and analysis of data collected under ADC Therapeutics Protocol ADCT-402-203. The company decided to discontinue the study on 20 Jul 2023. Given the challenges of defining the addressable segment of this difficult-to-treat patient population, the benefit-risk profile does not support continuation of the LOTIS-9 trial. So not all the analyses specified in study protocol are covered by the SAP. Analyse of PK/Biomarker data will be covered in separate SAP if needed.

This SAP should be read in conjunction with the study protocol and case report form (CRF). This version of the plan has been developed using the Protocol Amendment 3 08 August 2022 and CRF version dated 02 Feb 2023.

2 Study Objectives

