2.1 Primary Objectives

Cohort A

- To assess the efficacy of a response-adapted treatment of Lonca-R in unfit patients with previously untreated DLBC, or HGBCL, or Grade 3b FL

Cohort B

[figure not shown]
- To assess the tolerability and efficacy of a response-adapted treatment of Lonca-R in frail patients or patients with cardiac comorbidities with previously untreated DLBCL who are ineligible for standard R-mini-CHOP

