2.2 Secondary Objectives

Cohort A and Cohort B

- Further evaluate the efficacy of Lonca-R
- To characterize the safety profile of Lonca-R
- To characterize the PK profile of Lonca when given in combination with rituximab
- To evaluate the immunogenicity of Lonca when given in combination with rituximab
- To evaluate the impact of Lonca-R treatment on treatment-related and disease-related symptoms, patient-reported functions, and overall health status

Due to early termination of the study, patients are not followed up for sufficient time. Some endpoints for secondary objectives, such as progression-free survival (PFS), overall survival (OS) and patient reported outcome (PRO), will not be analyzed because of lack of sufficient follow up.

[figure not shown]
3 Study Design

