3.2 Sample Size Consideration

A sample size of 40 patients for each cohort is considered adequate to assess safety and efficacy in the corresponding study population. The percentage of ORR and CR rate with its 95% CI will be presented

descriptively. The primary endpoint, CRR, will be calculated based on the exact Clopper-Pearson Method.

Number of Patients	Number of CRs	CRR	Confidence intervals based on exact Clopper-Pearson method		
			90% CI for CRR	95% CI for CRR	99% CI for CRR
40	12	30%	(18.3, 44.0)	(16.6, 46.5)	(13.4, 51.4)
40	16	40%	(26.9, 54.2)	(24.9, 56.7)	(21.0, 61.4)
40	20	50%	(36.1, 63.9)	(33.8, 66.2)	(29.5, 70.5)
40	24	60%	(45.8, 73.1)	(43.3, 75.1)	(38.6, 79.0)

As of 20 Jul 2023 when decision was made to discontinue the study, 41 patients were enrolled and treated in total.

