3.4 Modifications to the statistical section of the protocol

Not applicable

4 Statistical Methods

All analyses will use SAS® version 9.4 or higher.

Categorical data will be presented using counts and percentages, with the number of patients in the analysis population as the denominator for percentages. Percentages will be rounded to 1 decimal place and not be displayed for zero counts.

Continuous data will be summarized using the number of observations (n), mean, standard deviation (std), median, minimum, and maximum. Minima and maxima will be rounded to the precision of the original value, and means, medians, and 95% confidence intervals (CIs) if presented will be rounded to 1 decimal place greater than the precision of the original value. The std will be rounded to 2 decimal places greater than the precision of the original value, up to a maximum of 3 decimal places.

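### The Cohort B co-primary endpoint of tolerability has no specified analysis, and the SAP does not name it as dropped

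*SAP*

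**What the plan says.** Protocol Table 3 lists two co-primary endpoints for Cohort B. One is CR rate. The other is "Tolerability as defined by the percentage of patients completing a total of 4 cycles of therapy divided by the total number of patients". SAP 2.1 carries the aim forward as a Cohort B primary objective: "To assess the tolerability and efficacy of a response-adapted treatment of Lonca-R in frail patients or patients with cardiac comorbidities".

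Protocol Section 9 leaves the detailed methods to the SAP. Its own efficacy subsections, 9.7.1 to 9.7.5, cover CR rate, ORR, duration of response, 2-year PFS and 3-year OS. Protocol 9.4 commits the study report to all efficacy and safety endpoints.

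The SAP reflects the sponsor's decision of 20 July 2023 to stop the study. SAP 1 gives a general warning: "So not all the analyses specified in study protocol are covered by the SAP". SAP 2.2 is more specific: "Some endpoints for secondary objectives, such as progression-free survival (PFS), overall survival (OS) and patient reported outcome (PRO), will not be analyzed", because follow-up is too short. SAP 3.2 speaks of a single primary endpoint: "The primary endpoint, CRR, will be calculated based on the exact Clopper-Pearson Method". SAP 4.8 states "The endpoints for efficacy include Complete Response Rate (CRR), Overall Response Rate (ORR) according to the 2014 Lugano classification as determined by investigator", with duration of response as the only addition. SAP 3.4, headed "Modifications to the statistical section of the protocol", is marked as not applicable.

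**The concern.** Tolerability is half of the primary question in Cohort B, the frail and cardiac-comorbid group. The sponsor's stated reason for stopping was that benefit-risk did not support going on, given the difficulty of delimiting the patients to be treated. Whether such patients could get through treatment is therefore a result that readers of the report will look for.

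The SAP keeps the objective but provides no estimate for it, and nothing tells the reader that this is deliberate. Anyone wanting the figure would have to assemble it from exposure and disposition tables, using a rule for a completed cycle that would be chosen after data from an open-label study are known.

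**Working it through.** **1. Is there an analysis anywhere?** The places where one could stand are:

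| Place | What it covers | Tolerability analysis? |
|---|---|---|
| Protocol 9.1 | Precision table for CR rate | No |
| Protocol 9.4 | General promise to report all endpoints | No method |
| Protocol 9.6 | Exposure | No |
| Protocol 9.7.1–9.7.5 | CR rate, ORR, DoR, PFS, OS | No |
| Protocol 9.8 | Safety | No |
| SAP 3.2 | CR rate as the primary endpoint | No |
| SAP 4.2 | Reasons for leaving treatment or study | Related counts only |
| SAP 4.7.1 | Number of cycles dosed | Related summary only |
| SAP 4.8.1–4.8.3 | ORR, CR rate, DoR | No |
| SAP 4.9 | Adverse events, deaths, laboratory, ECG and other safety data | No |

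None specifies the Cohort B proportion completing four cycles.

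**2. Is it declared as dropped?** SAP 1 names no endpoint. The list in SAP 2.2 is open-ended, but it is confined to secondary objectives and so cannot contain a co-primary endpoint. Its reason, short follow-up, also fits poorly. With 21-day cycles, Cycle 4 Day 1 falls nominally on day 3 × 21 + 1 = 64, and Cycle 4 ends on day 4 × 21 = 84. PFS and OS need 2 and 3 years.

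**3. Can the figure be derived without a further rule?** Not fully. In Cycle 1 rituximab is given on Day 1 and loncastuximab tesirine on Day 2 (Protocol Table 4). SAP 4.9.1.1 tabulates events leading to discontinuation of either drug. Neither document says whether a cycle in which only one drug was given counts as completed, or how patients still on treatment when the study was stopped are to be handled.

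**4. Precision.** The documents give exact intervals for CR rate only. The Clopper-Pearson 95% limits for x out of n are

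- lower = 2.5% quantile of Beta(x, n − x + 1)
- upper = 97.5% quantile of Beta(x + 1, n − x)

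At n = 40 this gives, for 12, 16, 20 and 24 events: 16.6–46.5, 24.9–56.7, 33.8–66.2 and 43.3–75.1. All four match Protocol Table 7 and the table in SAP 3.2. The SAP's 90% and 99% intervals also reproduce.

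The same formula applied to tolerability needs the Cohort B size, which is not given. SAP 3.2 reports only that 41 patients were treated in total. The table below assumes 60% completion and a range of n; n = 40 is the planned size and would leave one patient in Cohort A.

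| Assumed n | Completers | Exact 95% CI (%) | One patient = 100/n (points) |
|---|---|---|---|
| 10 | 6 | 26.2–87.8 | 10.0 |
| 20 | 12 | 36.1–80.9 | 5.0 |
| 30 | 18 | 40.6–77.3 | 3.3 |
| 40 | 24 | 43.3–75.1 | 2.5 |

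The intervals show how imprecise the result would be. They do not measure the defect. The last column shows how far each patient classified by an unstated rule would move the estimate.

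**The case against.** The best defence is that the figure is nearly recoverable. Protocol Table 3 gives the numerator and denominator, SAP 4.1.1 names the All-Treated Population for the primary analyses, SAP Section 4 has a general rule for counts and percentages, and SAP 4.7.1 summarises cycles dosed. SAP 1 openly warns of incomplete coverage. The study is descriptive, with no test or success threshold for tolerability, and neither document promises it a confidence interval. The treatment descriptions define a cycle as both drugs, so the one-drug ambiguity is an inference, and nothing shows that any patient's status depends on it. SAP 2.2 never applies the follow-up argument to tolerability. Finally, SAP 3.4 concerns the protocol's statistical section, which contains no tolerability analysis to modify, and the loss of PFS and OS is disclosed in SAP 2.2.

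Some of this stands. The endpoint itself is defined; what is missing is its analysis. The interval is a recommendation, consistent with the method used for CR rate. The effect of a one-drug rule is a possibility of unknown frequency.

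The rest does not remove the problem. A general rule for categorical data and a summary of cycles dosed do not create a named Cohort B output. The warning in SAP 1 does not tell a reader that a co-primary endpoint is gone. Protocol 9.4 is part of the statistical section, so leaving out a co-primary endpoint departs from it. SAP 3.4 is inaccurate in any case, because the analyses in Protocol 9.7.4 and 9.7.5 will not be done.

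**Conclusion.** The concern holds. One of the two Cohort B co-primary endpoints has no specified estimate, interval or completion rule in either document, and its absence is neither declared nor explained. This is more than missing detail: a team that followed the SAP exactly would produce no labelled tolerability result while still listing tolerability as a primary objective. It must be fixed.

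This conclusion rests on the text alone. Only the illustrative precision depends on assumptions, namely 60% completion and a Cohort B size between 10 and 40.

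**What to change.** - **Add a SAP subsection for the Cohort B co-primary tolerability endpoint.** Population: All-Treated, Cohort B. Estimate: number completing at least four cycles divided by number treated, with an exact 95% Clopper-Pearson interval. Saying at least four makes explicit that patients who go on to six cycles count as completers. State whether a completed cycle requires both drugs, and how patients on treatment when the study was stopped are counted.
- **Add a supplementary split of non-completers by recorded reason:** adverse event, death, patient or investigator decision, progression or non-response, sponsor termination. Under the Table 3 definition all of these are in the denominator and none in the numerator, so the raw proportion mixes toxicity with other causes. The split leaves that definition unchanged.
- **Replace the entry in SAP 3.4** with a list of the analyses changed or dropped, including PFS and OS. If tolerability is to be dropped, say so there and give the reason.

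The cost is one subsection, one table and a corrected entry, using cycle and discontinuation data already collected. Study conduct does not change.

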4.8.1 Overall Response Rate

Overall response rate (ORR) is defined as the proportion of patients with a BOR of complete response (CR) or partial response (PR) as determined by the investigator according to the 2014 Lugano classification criteria before the start of subsequent anticancer therapy or procedure. For the ORR analysis in the all-treated population, patients with a CR or PR will be counted as successes and all other patients (including those with missing response information) will be counted as failures.

A BOR of SD can only be made after the patient is on-study for a minimum of 35 days after the first dose of study drug. Any tumor assessment indicating SD before this time period will be considered as NE for BOR if no assessment after this time period is available.

The overall response rate and the corresponding 95% two-sided exact confidence interval will be presented.

4.8.2 Complete Response Rate

Complete response rate (CRR) is defined as the proportion of patients with a BOR of complete response (CR) as determined by the investigator according to the 2014 Lugano classification. The percentage of CRR with its 95% CI will be presented

4.8.3 Duration of Response

Duration of response (DoR) is defined for patients with CR or PR only as the interval between the date of initial documentation of a response and the date of the first documented evidence of progressive disease (based on radiographic or clinical progression at end of treatment [EOT]/end of study [EOS]) or death due to any cause, whichever occurs first. Patients who have the event after the start of subsequent anticancer therapy/procedure, or are progression-free and alive at the time of clinical cut-off, or have unknown status, will be censored at the last valid tumor assessment on or before the start of subsequent anticancer therapy/procedure or clinical cut-off time. When a subsequent anticancer therapy is used and progressive disease

(based on radiographic or clinical progression at EOT/EOS) is observed within 6 days, they will be considered as the same visit (within the protocol specified +/-6 days visit window) and the patient will be counted as having an event (losing the response).

Patients with no post-baseline disease assessment will be censored on Day 1.

Duration of response will be estimated and displayed for the all-treated population using Kaplan-Meier methods (SAS® PROC LIFETEST). A Kaplan-Meier plot will be presented.

4.9 Safety Analyses

All safety analyses will be based on the all-treated population.

General common rules

All safety analyses will be performed on the all-treated population, unless otherwise specified, using the following common rules:

- The baseline value is defined as the last non-missing value or measurement taken up to the first dose in the study.
- The analyses of the safety variables will be essentially descriptive and no systematic testing is planned.

4.9.1 Adverse Events, Serious Adverse Events, and Deaths

4.9.1.1 Analyses of Adverse Events

An AE is defined as any untoward medical occurrence in a patient or clinical investigation subject administered a pharmaceutical product, which does not necessarily have to have a causal relationship with this study treatment.

A treatment-emergent AE (TEAE) is defined as an AE that occurs or worsens in the period extending from the first dose of study drug to 15 weeks after the last dose of study drugs in this study (either loncastuximab or Rituximab) or start of a new anticancer therapy, whichever is earlier. The primary focus of adverse event reporting will be on TEAEs.

AEs will be coded according to MedDRA Version 24.1, and the severity of the toxicities will be graded according to the National Cancer Institute (NCI) Common Terminology Criteria for Adverse Events (CTCAE) Version 5.0, where applicable.

The summary of overall TEAEs includes:

- TEAEs
- Drug-related TEAEs (loncastuximab tesirine or Rituximab)
- Grade ≥ 3 TEAEs
- Drug-related Grade ≥ 3 TEAEs (loncastuximab tesirine or Rituximab)
- Serious Adverse Events (SAEs)

- TEAEs leading to dose delayed, reduced or interrupted (loncastuximab tesirine or Rituximab)
- TEAEs leading to discontinuation of loncastuximab tesirine or Rituximab
- TEAEs leading to death
- Infusion related reaction

The incidence of TEAEs will be summarized by system organ class (SOC) and preferred term (PT). A patient will be counted only once within a SOC and PT, even if the patient experienced more than one AE within a specific SOC and PT.

- All TEAEs \geq Grade 3 by PT, showing number (%) of patients with at least one TEAE, sorted by decreasing incidence of PTs
- All TEAEs by primary System Organ Class (SOC) and PT, showing number (%) of patients with at least one TEAE, sorted by SOC in alphabetic agreed order and decreasing incidence of PTs within SOC. This sorting order will be applied to all other tables, unless otherwise specified.
- All TEAEs by primary SOC, PT and Maximal CTCAE grade, showing number (%) of patients with at least one TEAE, sorted by SOC and PT in alphabetic order. This sorting order will be applied to all other tables, unless otherwise specified.
- All TEAEs \geq Grade 3 by primary SOC, PT and Maximal CTCAE grade
- All related TEAEs by primary SOC, PT and Maximal CTCAE grade (including possibly related, probably related, or related)
- All TEAEs leading to treatment withdrawal by primary SOC, PT and Maximal CTCAE grade
- All TEAEs leading to dose delay by primary SOC, PT and Maximal CTCAE grade
- All TEAEs leading to dose reduction by primary SOC, PT and Maximal CTCAE grade
- All TEAEs leading to infusion interruption by primary SOC, PT and Maximal CTCAE grade
- All TEAEs with fatal outcome by primary SOC, PT and Maximal CTCAE grade
- All Serious TEAEs by primary SOC, PT and Maximal CTCAE grade
- All infusion related reaction TEAEs by primary SOC, PT and Maximal CTCAE grade
- Summary of grouped TEAEs selected by Standardised MedDRA Query (SMQ), ADCT modified SMQ will also be provided by primary Grouped terms, PT and Maximal CTCAE grade.

Listing of all AEs, including non-TEAEs, will be provided. Besides, TEAEs leading to dose reduced, delayed or interrupted (loncastuximab tesirine or Rituximab), TEAEs leading to

discontinuation of loncastuximab tesirine or Rituximab, and TEAEs leading to death will also be provided.

